Study Protocol and Statistical Analysis Plan

Hearing Aid Quality and Reliability Study

Version 1.0

05/12/2021

Version 2.0

03/01/2023

NCT04995666

Protocol Title

Hearing Aid Quality and Reliability Study

1 Background

Audeo Life is a new hearing aid designed to be waterproof. This additional waterproofing is the result of two key hardware changes: the internal components of Audeo PL coating and the charging posts have been replaced with an inductive charging system. Because there have been no changes to the function of the hearing aids themselves, there should be no difference in performance expected between the two technologies (Audeo Life and the existing Audeo P). However, we have no data on the physical durability and reliability of the Audeo Life outside of Laboratory Tests. The purpose of this study is to check the quality of the Phonak Audéo Life and the Charger Case Go to react to any critical issues prior to launch.

2 Objectives

The primary objective of this study is to confirm that for adults with mild to severe hearing loss, the Phonak Audéo Life functions as expected in terms of performance compared to baseline performance testing performed in Visit 1 as measured by electroacoustic evaluation using a test box measurement at user gain.

3 Description of the investigational device

The investigational device will be used according to its intended use to amplify and transmit to the ear and thereby compensate for impaired hearing. The fitting of the investigational device will be according to clinical practice by trained and qualified audiologists. This device is an additional product in the Paradise line. This is a new hearing aid designed to be waterproof. The device will be worn most waking hours in most daily activities, including showering, bathing, swimming, exercising and while perspiring.

4 Design of the clinical investigation

This clinical investigation is an interventional study, executed at one investigation site, with a confirmatory design. The investigation model is a single group and there is no masking (un-blinded).

5 Risks and benefits of the investigational device and clinical Investigation

There are minimal risks associated with both the investigational devices and participating in the clinical investigation. Identified risks are no greater than those associated with the daily use and wear of approved, available hearing aids.

6 Endpoints

The primary endpoint is an electroacoustic measurement of hearing aid function after a 90 day period of wearing the devices. The study may reveal that the product is robust and can

withstand adverse environments on human subjects. Conversely, it may reveal that the devices do not maintain their performance after being subjected to real-world, life situations. This may, in turn, delay development and/or launch of the intended product.

7 Inclusion and Exclusion Criteria

Inclusion criteria:

- N2, N3, or N4 sensorineural hearing loss
- Adult age 18 or older
- Participant must be willing to wear RIC devices in as many physically active environments as possible including showering and bathing

Exclusion criteria:

- Diagnosis that may cause fluctuations in hearing
- Unable to tolerate the physical fit of a RIC device coupled with standard silicone domes
- Inability to be seen for 3 lab visits

8 Measurements and procedures

Visit 1: (Day 1) 20 participants will be invited to the study based on their hearing loss experience. Researcher will obtain an updated audiogram, if last audiogram obtained is older than 1 year. Participants will be fitted with a pair of investigational devices and a charger case. They will be instructed on use and care of the hearing aids and charger case. Participants will be instructed to use them in a variety of specific environments including while showering/bathing, exercising, while in pool, golfing, etc. Electroacoustic evaluation will be conducted on the hearing aids at Test settings and at User Gain settings for baseline information. Participants will be provided questionnaires for the home trial.

Visit 2: (Day 45) Participants will be asked if they have experienced any issues with hearing performance or sound quality (including feedback or gain changes) during the home trial. Participants will be asked to identify their charging behavior, including the number of charges from the onboard battery alone. Participants will be asked to provide any additional feedback regarding the hearing aids and charger case. Participants will be asked to rate the ease of use of the hearing aids and charger case. Participants will be asked to rate their comfort level wearing the hearing aids during the requested activities. They will be asked to rate their overall satisfaction with the hearing aids, charger case, and the combined system so far. If the participant requests any fine-tuning or adjustment to the hearing aid settings, they can do so at this time. . Electroacoustic evaluation will be conducted on the hearing aids at Test Settings and compared to the baseline testing.

Visit 3 (Day 90): Participants will come to the clinic to return the hearing aids and charger case. Datalogging information will be downloaded from the hearing aids to verify wearing times. Participants will be asked the same questions as on Visit 2. Electroacoustic evaluation will be conducted on the hearing aids at Test Settings and User Gain settings and compared to the baseline testing.

9 Statistical design and analysis plan

All subjects are exposed to the same treatment for the same total duration. As such, all subjects will be treated as a single cohort for analysis. The primary endpoint will be defined as a binary variable indicating whether the device performance has degraded as defined by comparing electroacoustic analysis (per ANSI S3.22-2014). Indicator of performance degradation in this investigation is: equivalent input noise (EIN) beyond the value specified on the product data sheet. All devices will be confirmed to comply with the data sheet prior to being dis-

pensed in the study. Devices which fail testing at the conclusion of the study will be recorded as a failure.

A device failure rate will be calculated as the percentage of all devices dispensed during the study which failed ANSI S3.22-2014 testing (on EIN) at the conclusion of the 90 day field trial. This value will be compared to the acceptance criterion of a 10% failure rate using a one sample binomial exact test. A p-value of less than 0.05 will indicate a statistically significant deviation in the sample from the acceptance criteria. **An observed failure rate significantly higher than 10% will indicate a failed acceptance criterion. An observed pass rate of 95% or higher will indicate a definitive pass acceptance criterion. In either of these cases, no statistical analysis will be necessary.**

Additional qualitative data will be collected regarding the participants' experiences, which will not be subjected to statistical analysis but will be summarized into key findings for the purpose of the study report.

10 Investigation Duration

The expected duration of each participant's participation is 90-100 days. The total expected duration of the clinical investigation is 15 weeks.

11 Data Handling and Management

Study data is recorded both with paper and with electronic Case Report Forms (p/eCRF). For each enrolled study participant a CRF is maintained. All CRFs are kept current to reflect the subject's status at each phase during the course of study. Participants cannot be identified in the CRF by name or initials and birth date but an appropriate coded identification is used. All study team members are authorized for the CRF entries and it is assured that any authorized person can be identified both for pCRFs and eCRFs. If pCRFs are used, the investigator's acronym as well as the subject ID is filled in and data are entered into an electronic file for analysis by the respective investigator and data get monitored by the assigned monitor. In case of a self-evident corrections, either the subject does it by himself or the investigator undertakes the correction by crossing out the word/sentence with a single horizontal line and by adding the correction including his personal identifier and the date.

Source documents for this investigation include, audiograms, Target fitting files, appointment checklists, and ANSI test measurement information and REM data.

All paper data will be stored in a locked filing cabinet at the Phonak Audiology Research Center (PARC). All electronic data files will be encrypted and stored on secure research computers. All identifying data will be stored at PARC.

The identifiable data kept at PARC will be destroyed as soon as the final analyses have been completed. The de-identified data will be kept for seven years after the publication of results. When the data are destroyed, paper records will be shredded by services provided at PARC. Electronic data will be encrypted as de-identified NOAH packages, where applicable, to be shared with Sonova Switzerland.

12 Amendments to the CIP

Amendments to the CIP, if necessary, will be updated with justification in this document.

The following amendments were added to version 2 of this document on 3/1/2023:

-In section 1.3, Measurements and Procedures, Visit 2: Added the step "electroacoustic evaluation will be conducted on the hearing aids at Test Settings settings and compared to

the baseline testing". This procedure, while not in the original CIP, was actually performed at the time of the study.

-Section 3.1, Preclinical Evidence and 3.2, Clinical Evidence to date:reference to the CER for Audeo P was added

-Section 5.3, Scientific Justification was added.

-Section 7.3.2 Primary analysis: Justification for not conducting a statistical analysis was added as the results revealed a 100% pass rate, and thus no statistical analysis was necessary.

13 Deviations from clinical investigation plan

Deviations from the CIP to protect the rights, safety and well-being of human participants under emergency circumstances may proceed without prior approval of the sponsor and the EC – such deviations will be documented and reported to the sponsor representative (Study Manager) and the EC as soon as possible. Apart from that the investigator is not allowed to deviate from this CIP unless that deviation does not influence the investigation data.

14 Device accountability

The PI or authorized designee keep records documenting the following in a written process:

- Names of participants who received, used, returned, or disposed of device
- Date of receipt, identification, and quantity of each investigational device (batch/serial number or unique code)
- Expiry date (if applicable)
- Dates of use
- Participant identification

15 Informed consent process

At the beginning of the first appointment, investigators will hand the consent form to the participant in a private setting and grant sufficient time to read the whole form. The consent form contains detailed information about incentives and reimbursement. Any questions will be answered and the participant will be given sufficient time to decide whether or not they want to participate in the study. After the participant signed two copies of the consent form, the researcher will sign both copies as well and provide one copy to the participant. In case of changes to the procedures described in the consent form, the participant will be informed at the beginning of an appointment.

Informed Consent will only be obtained by investigation participants who can provide informed consent themselves before enrollment.

16 Adverse events, adverse device effects and device deficiencies

Device deficiencies and all **adverse events (AE)** including all **serious adverse events (SAE)** are collected, fully investigated and documented in the source document and appropriate case report form (CRF) during the entire investigation period, i.e. from participant's informed con-sent until the last protocol-specific procedure, including a safety follow-up period (ISO_14155, 2020). Documentation includes dates of event, treatment,

resolution, assessment of serious-ness and causal relationship to device and/or investigation procedure.

Information on AEs is systematically collected during the regular investigation visits, and phone calls (if applicable).

The causality assessment of the SAE will be conducted according to MDCG 2020-10/1 Safety Reporting in Clinical Investigations of Medical Devices under Regulation (EU) 2017/745.

The reporting of Serious Adverse Events and Device Deficiencies follows the Regulation (EU) 2017/745 and the MDCG 2020-10/1 Safety Reporting in Clinical Investigations of Medical Devices under Regulation (EU) 2017/745.

17 Vulnerable Populations

The investigation does not include any vulnerable populations.

18 Suspension or premature termination of the clinical investigation

The clinical investigation will be suspended or prematurely terminated if the feature and/or investigative device malfunctions or if the participants or researchers are exposed to safety risks other than those outlined in this document. These events may include but are not limited to – natural disaster, widespread outbreak of illness, compromised structure of the investigation site, etc. The trial will be suspended within 5 days of determination that the study or device puts subjects at an unreasonable risk (per 21 CFR 812).

There is a blinding code kept electronically with the study materials. This code can be used to link the participant with their study ID, if needed.

According to the FDA, follow-up is required for participants who experience serious adverse events. Follow-up will be conducted by the study manager until the nature of the event is resolved.

19 Publication policy

The clinical investigation will be registered in clinicaltrials.gov, a publicly accessible database, as required by US law.

The results of the clinical investigation will be documented internally in a study report.

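### The primary objective is user-gain performance against Visit 1, but the only pass/fail rule in the public text is EIN against the data sheet, so the pass rate alone cannot confirm the objective

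*Combined protocol and SAP*

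**What the plan says.** Section 4 states: "This clinical investigation is an interventional study, executed at one investigation site, with a confirmatory design". Section 2 gives the primary objective as confirming that the device functions as expected, "compared to baseline performance testing performed in Visit 1 as measured by electroacoustic evaluation using a test box measurement at user gain".

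Section 6 is general: "The primary endpoint is an electroacoustic measurement of hearing aid function after a 90 day period of wearing the devices". It names no parameter, setting or comparator.

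Section 9 makes the endpoint binary (degraded or not, by comparing electroacoustic analysis under ANSI S3.22-2014) and then names one indicator: "Indicator of performance degradation in this investigation is: equivalent input noise (EIN) beyond the value specified on the product data sheet". The failure rate is the share of all dispensed devices that fail on EIN at the end of the 90-day trial. It is compared with 10% by an exact binomial test, and an observed pass rate of at least 95% is a definitive pass. Section 9 also requires each device to meet the data sheet before it is dispensed.

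Section 8 gives the measurements. At Visit 1, "Electroacoustic evaluation will be conducted on the hearing aids at Test settings and at User Gain settings for baseline information". At Visit 2, participants are asked about "any issues with hearing performance or sound quality (including feedback or gain changes) during the home trial", and "If the participant requests any fine-tuning or adjustment to the hearing aid settings, they can do so at this time"; the devices are tested at Test Settings only. At Visit 3 both settings are tested and compared with baseline.

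Section 12 reports a 100% pass rate as the reason for doing no statistical analysis. It does not say which parameter the rate refers to.

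**The concern.** The objective and the pass/fail rule differ in what is measured (performance at user gain, or EIN) and in the comparator (the device's own Visit 1 result, or a fixed specification limit). A confirmatory study needs its primary decision rule to answer its primary question. Here the rule can be met in full while the stated question stays open.

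The study exists because Section 1 says there are no durability data outside laboratory tests, and Section 6 asks whether devices keep their performance in real use. A loss of user-gain response, or a rise in EIN that stays within specification, is relevant to that question, and the failure rate registers neither. At stake is what the internal study report (Section 19) may claim from a 100% pass rate.

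**Working it through.** The question is which variable is measured, so the main check sets the sections side by side.

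| | Section 2 (objective) | Section 8 (Visit 3) | Section 9 (pass/fail) |
|---|---|---|---|
| Quantity | Performance in the test box | Electroacoustic evaluation, parameters not named | EIN only |
| Setting | User gain | Test Settings and User Gain | Not stated beyond the ANSI reference |
| Comparator | Visit 1 | Baseline testing | Data-sheet value |
| Tolerance | None | None | The data-sheet value |
| Enters the failure rate | – | No | Yes |

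Section 6 fits either reading. It is vague and does not conflict with the others, so the real tension is between Sections 2 and 9.

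**What the rule can and cannot detect.** For one device, let E1 and E3 be EIN at Visits 1 and 3, L the data-sheet limit, and G1 and G3 any user-gain result at the two visits. The device fails if E3 is beyond L. The pre-dispensing check ensures that E1 is within L.

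- If EIN rises from E1 to E3 but stays within L, the device passes. The undetected rise can be as large as L − E1. The documents give neither figure.
- If G3 is worse than G1 and E3 is within L, the device passes whatever the size of G3 − G1, because G does not appear in the rule.
- If E1 is within L and E3 is beyond L, the device fails. This is the only change from baseline that the rule registers.

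**What the 100% can bear.** The plan gives no device count. If all 20 invited participants were fitted with a pair, 20 × 2 = 40 devices were dispensed. A 100% pass rate under Section 9 would then be 0 failures in 40, with a one-sided exact 95% upper bound on the EIN failure rate of 1 − 0.05^(1/40) = 7.2%. With the participant as the unit (complete dependence within a pair) it is 0 in 20, and 1 − 0.05^(1/20) = 13.9%. Both bounds concern EIN failure. Neither bounds the rate of user-gain change from Visit 1, because that variable is not in the outcome.

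**Fine-tuning.** Settings may be changed at Visit 2, but no user-gain measurement is specified there, so an adjusted device has no new user-gain baseline. For such a device G3 − G1 mixes adjustment with any degradation. Test Settings are measured at all three visits.

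**The case against.** The case for the plan has real strengths.

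- **EIN is a legitimate pre-specified choice.** Choosing one primary parameter is acceptable, and with the pre-dispensing check a Day 90 failure is a real change from compliant to non-compliant. Data-sheet compliance also partly expresses the idea in Section 2 of functioning as expected. This stands, and is why the endpoint should be kept. It does not turn a specification limit into a comparison with the device's own Visit 1 result.
- **The user-gain comparison is planned.** Section 8 collects User Gain data at Visits 1 and 3 and compares them. A reader might infer that following the plan leaves the objective wholly unaddressed. The documents do not support that: only the pass/fail result fails to answer it. What is missing is a parameter, a tolerance and a link to the criterion.
- **More detail may exist elsewhere.** Section 12 cites CIP section numbers, such as 5.3 and 7.3.2, that the public text does not have, and the content of ANSI S3.22-2014 is not in the documents. The standard may already fix the setting at which EIN is read. The reading of the 100% must therefore stay conditional on Section 9's rule having been the one applied.
- **No overclaim is shown.** No study conclusion appears in the documents. This stands, and it limits the severity.

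It is also tempting to size the defect by how many worsened devices would overturn the plan's verdict. With 40 devices, 3 failures would lose the definitive pass (37/40 = 92.5%), and 8 (one-sided p = 0.042) or 9 (two-sided p = 0.0155) would fail the criterion. Those counts only restate Section 9's thresholds. They need a rule that any worsening from Visit 1 is a failure, which the plan does not contain and under which ordinary test-retest variation would count. They do not measure the defect.

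**Conclusion.** The mismatch between Sections 2 and 9 is in the text. The pass/fail result alone cannot confirm the Section 2 objective. If the 100% pass rate was obtained under Section 9's rule, it supports one statement: EIN was within the data-sheet limit at Day 90.

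The number of devices that worsened but passed is unknown and cannot be computed from the documents. A reader might infer that devices did degrade unnoticed, or that the sponsor has claimed too much; the documents show neither.

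The conclusion rests on the public text alone and on Section 9 being the only pass/fail rule. It should be fixed, because it determines what the study report can say. It is not graded higher because no overclaiming conclusion is shown and the relevant measurements were planned.

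**What to change.** 1. Keep the pre-specified EIN endpoint. Word the primary conclusion as EIN compliance with the data sheet at Day 90, and do not present the Section 2 objective as confirmed by the pass rate. Reconcile Section 2 with Section 9, and date and label any rewording as made after results were known.
2. For every device, report the Visit 3 minus Visit 1 change in all electroacoustic parameters recorded at both visits, at Test Settings and at User Gain. Reporting all of them avoids selective choice now that results are known. Label this descriptive and post hoc, and set no new pass/fail limit. Show individual device values, since an average can hide a single failing device. A mean with a confidence interval is optional and should allow for two devices per participant, for example through participant means.
3. Identify the devices fine-tuned at Visit 2 (the Target fitting files are source documents under Section 11) and show them separately without dropping them. A request for adjustment may come from a degraded device, so exclusion could bias the picture toward no change. For these devices, read the Test Settings change alongside the user-gain change as the cleaner evidence, on the assumption that fine-tuning does not alter the Test Settings measurement.

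No new visits or measurements are needed: a narrower conclusion, a dated note, one table or plot, and a check of the fitting files. The downsides are a more limited primary claim, descriptive evidence only, and dependence on retained coded records. Section 11 has identifiable data destroyed once final analyses are complete and de-identified data kept for seven years after publication. It does not say whether the latter include the fitting files. If the user-gain data cannot be recovered, item 1 can still be done.

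### The binomial fail test treats the two devices of one wearer as independent; read one-sided with 20 pairs, its false-fail rate passes 5% once the within-wearer ICC exceeds about 0.10

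*Combined protocol and SAP*

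**What the plan says.** Section 9 defines the estimate per device: "A device failure rate will be calculated as the percentage of all devices dispensed", a failure being an equivalent input noise (EIN) result outside the data sheet value at the end of the 90-day trial. On the test it says: "This value will be compared to the acceptance criterion of a 10% failure rate using a one sample binomial exact test".

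Two further sentences bear on direction. The first is neutral: "A p-value of less than 0.05 will indicate a statistically significant deviation in the sample from the acceptance criteria". The second is directional: "An observed failure rate significantly higher than 10% will indicate a failed acceptance criterion". Neither says whether the p-value is one- or two-sided. A separate rule in the same section declares a pass when at least 95% of devices pass, with no test.

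Section 8, Visit 1, sets the sample: "20 participants will be invited to the study based on their hearing loss experience", and "Participants will be fitted with a pair of investigational devices and a charger case". That makes 20 pairs, or 40 devices. The number finally enrolled is not given.

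Section 9 treats all subjects as one cohort because treatment and duration are the same for everyone. It has no cluster term, participant-level rule or other allowance for two devices sharing a wearer. Section 12 records that every device passed and that no test was run.

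**The concern.** An exact binomial test holds its level only if the units are independent. Here the two devices of a pair share one wearer's water, sweat and exercise exposure, and one charger case. Exposure is largely left to the wearer. Section 7 asks for this: "Participant must be willing to wear RIC devices in as many physically active environments as possible including showering and bathing". Wearing time is checked only at Visit 3: "Datalogging information will be downloaded from the hearing aids to verify wearing times". If heavy users tend to lose both devices and light users neither, failures cluster within wearers. The failure count then varies more than the binomial allows, and a high count arises by chance more often than the p-value says.

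At stake is a false fail verdict on a device whose true failure rate is at the 10% criterion. The planned test also cannot tell eight affected wearers from four: 8 failures of 40 give the same p-value either way.

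**Working it through.** **Inputs.** Null failure rate 10%, threshold 0.05 and the device as unit (Section 9); 20 participants with two devices each (Section 8). The documents give no within-wearer correlation, so the ICC is an assumption, ranged from 0 to 1. The value 1 is a bound at which pairs never disagree. Pairs are taken as complete.

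**Step 1: the plan's own level, under independence.** With 40 devices, P(X ≥ 8) = 0.042 and P(X ≥ 7) = 0.100, so the one-sided rule fails the device at 8 or more. The 0.05 threshold is respected.

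**Step 2: pair model.** For failure rate p:
- P(both fail) = p² + ICC·p(1−p)
- P(exactly one fails) = 2p(1−p)(1−ICC)

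At p = 0.10 the probabilities of (both, one, none) are (0.010, 0.180, 0.810) at ICC 0, (0.055, 0.090, 0.855) at ICC 0.5 and (0.10, 0, 0.90) at ICC 1. The variance of the total is 40 × 0.09 × (1+ICC): 3.6, 5.4 and 7.2. Convolving over the pairs gives the exact distribution of the number of failures.

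**Step 3: one-sided false-fail rate at a true 10%.**

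| Complete pairs | Fail at | ICC 0 | ICC 0.3 | ICC 0.5 | ICC 1 | Passes 5% at ICC about |
|---|---|---|---|---|---|---|
| 20 | 8 of 40 | 4.2% | 6.5% | 7.8% | 13.3% | 0.10 |
| 19 | 8 of 38 | 3.2% | 5.2% | 6.4% | 11.5% | 0.27 |
| 18 | 8 of 36 | 2.4% | 4.1% | 5.2% | 9.8% | 0.46 |
| 17 | 7 of 34 | 4.8% | 7.2% | 8.6% | 8.3% | 0.02 |

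The crossing point moves unevenly because the cutoff is an integer and the level attained at ICC 0 differs by row.

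**Step 4: two-sided reading, fail tail only.** With 40 devices, 8 failures give p = 0.057 and 9 give 0.015, so the cutoff is 9. The fail tail is 1.5 / 3.0 / 3.9 / 4.3% at ICC 0 / 0.3 / 0.5 / 1, with a peak of 5.1% near ICC 0.86. With 18 pairs, 8 of 36 already gives a two-sided p of 0.024. The cutoff is then the same as one-sided, and the 18-pair row applies.

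**Step 5: what the planned p-value cannot see.** Take 8 failures of 40, so the observed rate is 0.2 and N × rate × (1 − rate) = 6.4. Estimate ICC = 1 − (discordant pairs)/6.4, limited to 0 to 1. Set x′ = 8/(1+ICC) and N′ = 40/(1+ICC), and compute p = I₀.₁₀(x′, N′−x′+1), the regularised incomplete beta function.

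| Both fail / one fails | ICC estimate | p, pairs allowed for | p as planned |
|---|---|---|---|
| 0 / 8 | 0 (raw −0.25) | 0.042 | 0.042 |
| 1 / 6 | 0.0625 | 0.048 | 0.042 |
| 4 / 0 | 1 | 0.133 | 0.042 |

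**Step 6: does the adjusted test hold its level?** Enumerating all (both, one, none) counts, with the ICC estimated from each, gives these sizes at ICC 0 / 0.3 / 0.5 / 1:
- 20 pairs: 3.8 / 3.8 / 3.5 / 4.3%
- 19 pairs: 2.9 / 2.9 / 2.8 / 3.5%
- 18 pairs: 2.3 / 3.4 / 3.4 / 2.8%
- 17 pairs: 3.1 / 2.7 / 2.6 / 2.2%

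**Step 7: zero failures, as reported.** The ICC cannot be estimated. Solving [(1−p)² + ICC·p(1−p)]²⁰ = 0.05 gives a one-sided 95% upper limit of 7.2 / 8.5 / 9.6 / 13.9% at ICC 0 / 0.3 / 0.5 / 1. The limit reaches 10% at an ICC of about 0.57.

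**The case against.** The strongest reply is that this may never bite. The plan does not say the test is one-sided, and its wording on significance is neutral. Read two-sided at the planned 40 devices, the fail tail is within about 5.1% at every ICC. That stands for 40 devices. It is not a general protection, since at 18 pairs the two-sided rule also exceeds 5% from an ICC of about 0.46.

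Second, clustering is assumed. Shared exposure is plausible, but nothing in the documents links it, or the shared charger, to EIN. This stands. A reader might infer that any clustering breaks the 5% level. The figures do not support that: with 20 pairs an ICC below about 0.10 leaves it intact, and one double failure with six single ones leaves the verdict on 8 failures unchanged.

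Third, for a study meant to catch problems before launch, a liberal fail rule errs on the cautious side, and the adjustment gives up power. This also stands, and is the price of holding the stated level.

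Fourth, an effective-sample-size test with a plugged-in ICC is not exact and does not by itself cover unpaired devices. Both points are right, and the fix is worded accordingly.

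Finally, the plan sets no confidence-limit criterion, so the zero-failure limit corrects no stated rule. Agreed: it is a reporting addition only.

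**Conclusion.** The point holds as a minor one. The planned test ignores pairing. With 20 complete pairs and a one-sided reading, its false-fail rate exceeds 5% once the ICC is above about 0.10, reaching 7.8% at 0.5 and 13.3% at the bound. The size depends on three things the documents leave open: the sidedness, the number of pairs dispensed, and the ICC.

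A reader might go further and infer that the reported pass is unsound. The documents do not support that. With zero failures the fail test was not run, no p-value changes, and the error described works against the device rather than in its favour. What remains for the reported result is how firmly zero failures supports a true rate below 10%. That depends on the assumed ICC, but it is not a criterion of the plan.

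**What to change.** In Section 9:

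1. State that the fail test is upper-tail at 0.05.
2. Keep the device failure rate as the estimate.
3. Replace the independent-device test with the effective-sample-size binomial test of Step 5: ICC estimated from the complete pairs and limited to 0 to 1, failures and devices each divided by 1+ICC, p from the incomplete beta function. Describe it as approximate, with size at most about 4.3% by enumeration for 17 to 20 complete pairs.
4. Count any unpaired device as its own cluster. The enumeration does not cover this case.
5. Report the number of participants with at least one failed device.
6. With zero failures, show the one-sided 95% upper limit over ICC 0 to 1 (7.2% to 13.9% at 20 pairs) as a sensitivity display, not a decision rule.

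Since the study is complete, items 5 and 6 are what can be added to its report. Items 1 to 4 matter if this plan is reused for devices dispensed in pairs.

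The cost is a short SAP edit and a few lines of code, with no new data. The downside is power. At a true 25% failure rate with 20 pairs it falls from 82% to 80% at ICC 0, 78% to 72% at 0.3, 76% to 66% at 0.5 and 77% to 59% at 1. Unless the ICC is 0, the zero-failure limit is also less favourable than the independent-device figure of 7.2%.
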